We are conducting an epidemiological prostate cancer case-control study in Baltimore, Maryland. Participants will be African-American and Caucasian males who reside in Baltimore city and surrounding areas. The study is ongoing and will recruit 1000 prostate cancer cases and 1000 population-based controls. The cases are recruited at two Baltimore hospitals, the Veterans Affairs Medical Center and the University of Maryland Medical Center. Cases will have pathologically confirmed prostate cancer. The population-based controls are identified through the Maryland Department of Motor Vehicle database, and are frequency-matched by age and race to cases. Enrollment of controls started concurrently with case accrual. The first 12 months of the study constituted a pilot study, during which we evaluated the recruitment procedures. The study involves the administration of a survey and collection of blood from all study subjects. The survey evaluates family cancer history, tobacco use, medication, occupational history, socioeconomic status, and risk factors for prostate cancer. Freshfrozen tumor specimens will be obtained from cancer patients if available. The study is supported by an epidemiological infrastructure that has been developed by our resource contractor at the University of Maryland for a lung cancer case-control study. This lung cancer study is ongoing, and the controls that are recruited for the prostate cancer study are joint controls with the lung cancer study. Hence, population-based male controls recruited by our contractor have double eligibility for the concurrent lung and prostate cancer studies. To achieve an age and race matching of cases and controls in the prostate study, we will over-sample male controls in the lung study.

We will test the primary hypothesis that genes and environmental exposures, including infections and medical history, and interactions between these factors modify prostate cancer susceptibility and contribute to the excessive disease risk among African-American men. As the secondary goal, we will study gene expression profiles of prostate tumors to identify changes in tumor biology that are associated with exposure to genetic and environmental risk factors. It is a focus of this research to identify mechanisms in tumor biology that may cause the aggressive nature of prostate cancer in African-American men.

TABLE OF CONTENTS

1 1.1 1.2	INTRODUCTION STUDY OBJECTIVES BACKGROUND AND RATIONALE	5 7 8

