2.1 ELIGIBILITY CRITERIA

CASE SUBJECT SELECTION

We will recruit incident cases of pathologically confirmed PCa at all stages of the disease that are age 40 to 90 years. Treatment can be surgery or therapy. The following check list will be used to verify eligibility of a case subject.

ELIGIBILITY CHECK LIST - PROSTATE CANCER CASES

NAME_____

DATE_____

DATE OF BIRTH_____

ID# _____

Yes	No	Criteria (ALL MUST BE CHECKED)
		Has been diagnosed with prostate cancer within the last two years
		Pathological diagnosis of prostate cancer made at the local hospital
		pathology department
		Resides in Baltimore City or contiguous metropolitan counties, Anne
		Arundel and Prince George's counties, Eastern Shore, western and northern
		Maryland, or adjacent counties in Pennsylvania, Delaware, Virginia, or the
		Washington Metropolitan area
		Has a residential working phone within his home
		Born in the United States
		Of African-American or Caucasian descent, and age 40 to 90 years
		A non-objection statement by the physician from the hospital where the
		patient was identified, or listed as the treating physician by the tumor
		registry or surgical pathology report, to contact the patient
		Is not currently residing in an institution, such as a prison, nursing home, or
		shelter
		Is not a severely ill patient in the intensive care unit
		Speaks English well enough to be interviewed
		Is able to give informed consent
		Is physically and mentally capable of performing the interview
		Has never been interviewed as a control for this study
		Subject provides informed consent and signs form.
		UnwillingUnavailable

NCI IRB Approval:	October 28, 2004
Protocol Number:	05-C-N021

SELECTION OF POPULATION-BASED CONTROLS

Population-based controls will be identified through the Department of Motor Vehicles (DMV), and matched on age (5-year intervals), gender and race to cases. Recruitment of controls will start concurrently with case accrual, using the age and race frequency distribution of cancer patients in previous years, but recruitment objectives can be re-assessed to ensure a frequency-matched study. We will exclude controls that do not have a listed home phone number. The following check list will be used to verify eligibility of a control subject.

ELIGIBILITY CHECK LIST - POPULATION-BASED CONTROLS

NAME_____

DATE_____

DATE OF BIRTH_____

ID# _____

Yes	No	Criteria (ALL MUST BE CHECKED)
		Resides in Baltimore City or contiguous metropolitan counties, Anne

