3.1.5 LIMITATIONS OF THE CASE-CONTROL DESIGN

A frequent limitation of case-control studies is the heterogeneity of the population as it relates to race, age, and catchment area. If not addressed, the study may yield differences in genetic frequencies that are unrelated to the case status. To correct for the problem, we have restricted the study to a narrow geographic area, and will match for race and age by frequency. We have conducted a survey to determine the expected age range for cases. We anticipate a mean and median age of about 66 years for the prospective cases, which will permit an age matching with population-based controls using the established resources. Most patients will be in moderately good health, as they are identified at a relatively young age through PSA screening. Cases could be rendered more similar to controls with a selection criterion for controls that would achieve matching of cases based on census tract. This alternative would not eliminate a possible selection bias but would make the study substantially more difficult to perform. Also, our experience in Baltimore is that population control accrual is not skewed to one part of Baltimore. A 2002 survey for the ongoing lung cancer case-control study indicated that the recruited cases and population-based controls have a similar residential history. Thirty-eight percent of the cases were from Baltimore City versus 54% of the controls, and 62% of the cases lived in Baltimore suburbs or Eastern Shore counties versus 46% of the controls. We do not expect a selection bias based on genotype that would be confounded by behavior or education, as the genotype is unknown to the subjects and there is no plausible relation to either behavior or other factors that might affect the selection. A limitation common to other case-control studies is the possibility of differences between cases and the control population that are caused by a confounding disease, and not the disease under investigation (case identification among a hospitalized cohort, hospital-based controls). We are limiting the bias by matching cases with population-based, but not hospital-based, controls. The relatively young age of our cases will also limit this problem.

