5.4.2 AVAILABILITY OF CASES AND JUSTIFICATION OF SAMPLE SIZE

A review of cancer registry data shows that the 2 participating hospitals treated 313 PCa cases in 2001 of which 150 cases were identified as being of African-American and 143 cases as being of Caucasian descent (Table 8). Twenty cases were either not informative for race or had a different race/ethnic background (e.g., Asian, Hispanic). Most of the cases had residency in the greater Baltimore area. There were 52 known available cases with radical prostatectomy in 2001, which is sufficient to meet our goal of recruiting at least 25 cases with radical prostatectomy per year.

We will use the case-control design to detect statistically significant differences in the frequency of genotypes between PCa patients and randomly selected population-based controls that are matched by age, gender and race to the cases. For the initial analysis, all cases will be grouped together. We will then examine the study population stratified by race and/or exposure. The study is designed to detect risk associations that have odds ratios of ≥ 1.5 . Associations between PCa and genotypes of the angiogenesis and hormone pathways have been found to have odds ratios that are in the range of 1.5-2.5 (39,69-71). Examples are shown in Table 3. We are not aiming to detect weak risk associations that are reflected by odd ratios between 1 and 1.5. Such associations are prone to a selection bias and confounding, and would require a larger sample. Our proposed study is exploratory and designed to detect potentially novel genotype–cancer risk associations. The finding of a new disease-associated genotype can subsequently be validated in a larger study.

Known Available Cases by Hospital Calendar Year 2001					
	African-American Caucasian Total				
VA Hospital	85	48	133		
All Cases					
UM Medical Center	65	95	160^{-1}		
All Cases					
Total	150	143	293		
1 >70% of patients are from the greater Baltimore area					

Table 8: Known Available Cases from Hospital Tumor Registries

POWER CALCULATIONS

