wild-type genotype (major allele), or the lowest exposure subgroup, as the reference group. Odds ratios and 95% confidence intervals will be calculated by unconditional logistic regression. Regression analysis will be performed in univariate and multivariate models to assess associations between risk factors and cancer susceptibility, and to adjust for possible confounding factors. Case-case analyses, correlating tissue marker expression with tumor staging, hormone blood concentrations, diet or genotypes, will be done by ANOVA, with the student's t-test, or a nonparametric test, such as the Mann-Whitney U rank sum test. To look at trends, the Mantel-Haenszel test for trend will be used to assess the correlation between marker expression/frequency and categorized (e.g., low, medium, high) variables, such as tumor stage, intake of a dietary factor, or IGF-1 blood concentrations. The association between a genotype and outcome will be studied either in a logistic regression model after categorizing into a good and poor outcome group or with the Kaplan-Meier method and the log-rank test. All analyses will be performed with the STATA and SAS statistical software packages.

ANALYSIS OF GENE EXPRESSION PROFILES

The data from the Affymetrix HG-U133A array will be estimated using the RMA procedure from Bioconductor (www.bioconductor.org). Previous analysis on raw data from replicate samples with RMA indicates that the mean standard deviation of log2 intensities is 0.1 across all intensity levels. This corresponds to a typical technical error of 5%-10% (94).

The factorial study design suggests an analysis of variance. We will first examine the four groups for heterogeneity of variances by comparing the ratios of variances between groups to the F-distribution. If the distributions conform, we will follow standard ANOVA procedure. If there is significant departure from agreement, we will perform non-parametric ANOVA using the rank F-test and use the Welch t-test for two group comparisons. We will select differentially expressed genes for contrasts between racial groups at each level of tumor, and for the difference between tumor stages across racial groups. To address the multiple comparisons problem we will use a modified FDR procedure of Benjamini and Hochberg adapted to correlated data (95).

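### A large share of available cases is at a VA hospital and the share differs by race, but controls are general-population men and no analysis uses recruiting hospital or VA status, so exposures linked to VA use can appear as risk factors

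*Protocol*

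**What the plan says.** The precis states the case source: "The cases are recruited at two Baltimore hospitals, the Veterans Affairs Medical Center and the University of Maryland Medical Center". Section 2.1 states the control source: "Population-based controls will be identified through the Department of Motor Vehicles (DMV), and matched on age (5-year intervals), gender and race to cases". Section 5.4.2 describes the comparison as one with "randomly selected population-based controls that are matched by age, gender and race to the cases".

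Table 8 in section 5.4.2 gives the 2001 tumor registry counts of available cases by hospital and race (African-American, Caucasian, total): "VA Hospital 85 48 133" and "UM Medical Center 65 95", the latter totalling 160.

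Section 3.1.5 discusses heterogeneity of race, age and catchment area, residence, selection related to genotype, and differences caused by a confounding disease. On the last of these it says: "We are limiting the bias by matching cases with population-based, but not hospital-based, controls". It does not mention that one of the two case sources is a VA hospital.

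Section 5.4.3 first groups all cases together and then examines them by race. It adds: "Regression analysis will be performed in univariate and multivariate models to assess associations between risk factors and cancer susceptibility", with adjustment for possible confounders that are not named. Recruiting hospital, veteran status and VA use appear nowhere as a matching, stratification or adjustment factor.

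The precis puts environmental exposures, infections and medical history into the primary hypothesis, together with their contribution to the excess risk in African-American men.

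**The concern.** In a case-control study the controls should reflect the men who would have become cases at the recruiting hospitals had they developed the disease. A man becomes a VA case only if he uses the VA hospital. Controls drawn from a driver database contain VA users only in whatever proportion they occur there.

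The questionnaire covers tobacco, occupation, socioeconomic status, medication, medical history and sexual history. Several of these plausibly differ between VA users and other men. Any such difference enters the case-control contrast without any link to prostate cancer.

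The VA share of cases also differs by race, so the distortion need not be the same in the two races. The study could then report a race difference in an exposure effect that reflects only where cases were recruited. The pooled and race-stratified analyses in 5.4.3 would not show this, because neither separates the hospitals.

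**Working it through.** **Inputs from the protocol.** Table 8: VA 85 African-American and 48 Caucasian cases; University of Maryland (UM) 65 and 95. Table 7: 500 cases and 500 controls per race.

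**Assumed inputs (not in the protocol).** VA share among controls, 5% to 45%. Prevalence of an exposure with no effect on prostate cancer, 20% in men who do not use the VA and 35% in VA users. UM cases are treated as non-users of the VA. No adjustment.

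**Step 1: reproduce Table 8.** 85 + 48 = 133; 65 + 95 = 160; 133 + 160 = 293. Adding the 20 cases of other or unknown race gives 313, the total stated in 5.4.2.

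**Step 2: VA share of available cases.**
- All: 133/293 = 45.4%
- African-American: 85/150 = 56.7%
- Caucasian: 48/143 = 33.6%

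**Step 3: expected exposure prevalence.** Prevalence = 0.20 + 0.15 × VA share.
- African-American cases: 0.20 + 0.15 × 0.567 = 0.285, odds 0.3986
- Caucasian cases: 0.20 + 0.15 × 0.336 = 0.2503, odds 0.3340

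**Step 4: crude odds ratio for a null exposure**, with the same control VA share in both races:

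| Control VA share | Control prevalence | Control odds | OR, African-American | OR, Caucasian |
|---|---|---|---|---|
| 5% | 0.2075 | 0.2618 | 1.52 | 1.28 |
| 10% | 0.2150 | 0.2739 | 1.46 | 1.22 |
| 20% | 0.2300 | 0.2987 | 1.33 | 1.12 |
| 30% | 0.2450 | 0.3245 | 1.23 | 1.03 |
| 45% | 0.2675 | 0.3652 | 1.09 | 0.91 |

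When both races have the same control share, the control odds cancel from the comparison between races. The ratio of the two odds ratios is then 0.3986/0.3340 = 1.19 in every row. If exposure prevalence does not differ between VA users and others, every odds ratio is 1.00.

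**Step 5: different control shares by race.** Hold Caucasian controls at 10% (OR 1.22).
- African-American controls at 20%: OR 1.33
- At 30%: OR 1.23, so the race gap has almost gone
- At 35%: 0.3986/0.3378 = 1.18, so the order has reversed

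The break-even control odds are 0.2739 × 1.1936 = 0.3269, a prevalence of 0.2464, hence a VA share of (0.2464 − 0.20)/0.15 = 31%. That is about 21 points above the Caucasian share.

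**Step 6: what a split by hospital would show.** With 10% VA users among controls, UM cases against controls give 0.25/0.2739 = 0.91. VA cases against controls give (0.35/0.65)/0.2739 = 0.5385/0.2739 = 1.97. The contrast between hospitals is 0.5385/0.25 = 2.15 whatever the control share, so the split reveals a pattern that the pooled odds ratio conceals. The UM figure is not exactly 1 either, so UM cases are not an unbiased benchmark.

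**The case against.** - **The quoted sentence is correct for its purpose.** It answers the problem of a confounding disease in hospital-based controls, and population controls do limit that. A reader might infer that for VA cases these controls make matters worse, or that the sentence should go. The text does not support that; it simply does not address selection into VA care.
- **Only the case shares are documented.** The control VA share, the prevalences and the existence of any gap are assumed. DMV controls are not screened for veteran status and can include VA users, so the contrast is 45% against an unknown share, not against zero. It cannot be said that false associations *will* appear.
- **The odds ratios are crude.** Section 5.4.3 plans multivariate adjustment, and the questionnaire collects tobacco, occupation and socioeconomic status. Adjustment could remove part of the difference, though adjusting for the others may leave some of it when one of these is itself the exposure studied.
- **The race ordering is not established.** A reader might infer that the bias must be stronger in African-American men. That needs similar control VA shares in the two races; step 5 shows the gap closing and then reversing.
- **The design threshold of 1.5 is not generally reached.** A reader might infer otherwise from the table, but at a 10% control share the African-American figure is 1.46, and it passes 1.5 only in the 5% row.
- **Table 8 counts available 2001 cases.** It does not describe enrolled cases, and no hospital quota is set.
- **The study is largely genetic and described as exploratory.** This limits the consequence. Exposures and the African-American excess risk are nevertheless in the primary hypothesis of the precis.
- **The questionnaires and any separate analysis plan are not shown.** Military service may already be recorded.

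These points limit the size and certainty of the problem. They do not remove the mismatch between case and control source populations, which the protocol nowhere mentions.

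**Conclusion.** The point holds as a risk of bias that the plan does not address. The documented part is the 2001 VA share of available cases (45% overall, 57% African-American, 34% Caucasian), controls matched only on age, gender and race, and no use of recruiting hospital or VA status anywhere in the analysis.

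It follows that exposures differing between VA users and other men can appear as prostate cancer risk factors unless adjusted for, and can do so unequally by race. Under the illustrative assumptions and no adjustment, the distortion ranges from negligible to moderate. Its size, and the direction of any race gap, depend on the control VA share in each race and on the exposure contrast, and the protocol gives neither. Genotype main effects are little affected. The point concerns exposure, medical-history and race-by-exposure findings.

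**What to change.** 1. **Section 5.4.3.** For exposure and medical-history associations, add a pre-specified analysis of UM cases against controls and VA cases against the same controls, using a polytomous logistic model, overall and by race, with a test of heterogeneity between hospitals. State that an exposure effect or race difference that is not consistent across hospitals will be interpreted with caution. It should not be barred outright, because it may be real.
2. **Covariate.** Use military service or VA use, in cases and controls, as an adjustment or restriction variable if already recorded. Otherwise add one questionnaire item. VA use is the closer measure of the selection; military service alone would only partly capture it.
3. **Section 3.1.5.** Keep the sentence on confounding disease and add that population controls may not represent the VA hospital's source population.

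**Cost.** Recruiting hospital should already be known for each case, so step 1 needs no new data. Hospital-specific intervals will be wider. If enrolment follows Table 8, the 500 cases per race split into about 217 UM and 283 VA (African-American) and 332 UM and 168 VA (Caucasian). Taking interval width on the log scale as proportional to √(1/cases + 1/500), and assuming similar exposure prevalence, the intervals are about 29%, 18%, 12% and 41% wider than with all 500 cases. The only possible addition to data collection is one item.

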3.2 DRUG ADMINISTRATION

Not applicable for our study.

3.3 TREATMENT MODIFICATIONS

Not applicable for our study.

3.4 PHARMACOKINETIC STUDIES

Not applicable for our study.

3.5 **PROTOCOL EVALUATION**

Not applicable for our study.

3.6 CONCURRENT THERAPIES

Not applicable for our study.

3.7 SURICAL GUIDELINES

Not applicable for our study.

3.8 RADIATION THERAPY GUIDELINES

Not applicable for our study.

3.9 RADIATION THERAPY GUIDELINES

Not applicable for our study.

3.10 POST STUDY EVALUATION

Not applicable for our study.

4 **SUPPORTIVE CARE**

Not applicable for our study.

NCI IRB Approval:	October 28, 2004
Protocol Number:	05-C-N021

5 DATA COLLECTION AND EVALUATION

The University of Maryland contractor is responsible for the collection and evaluation of the study data.

5.1 DATA COLLECTION

All data will be entered and stored in a centralized case-control study database at the University of Maryland. [name], a software consultant to the Laboratory of Human Carcinogenesis, is assisting the contractor with database maintenance and upgrades. The centralized database consists of three databases, a tissue, a survey, and a tracking database, that are linked through unique identifiers. The tracking database contains the personal information of each study participants. Access to this database is strictly controlled, and the database is not accessible to NCI researchers. The tissue database is a tracking and inventory database for fixed and fresh-frozen tissues, and for blood samples. Updated files of the database are available to the NCI researcher. The survey database contains the demographic and epidemiological information of the study participants. Access to information in this database has to be requested. Information from the tissue and survey databases cannot be linked to any personal identifiers.

5.1.1 SURVEY DATA

Initially, all forms including the eligibility screener forms, consents, HIPAA authorization forms, interview forms, specimen collection forms, pathology and medical reports, etc., will be assigned a study ID number, which is common only to all forms and specimens that belong to one particular participant. All forms are then entered into the centralized case-control study database for tracking and storage. The forms are filed in locked file cabinets in the secured study office.

5.1.2 QUESTIONNAIRE DATA

The questionnaire data are entered into the survey database twice with a different data entry person each time. If a discrepancy occurs, a supervisor will verify the correct entry. Prior to entry, all questionnaires are coded and edited using a standardized code for occupation, illness, and medication. When appropriate, we utilize the ICD-9 codes (or further updated codes as they become available in the future). A coder will highlight all sections in a questionnaire that contain either an illogical response or missing data. The highlighted sections will be reviewed by a supervisor, or the Research Study Coordinator where needed. A patient may be re-contacted to clarify an answer or to complete a missing response. The supervisor will also examine the coding of about ten percent of the questionnaires. The questionnaires are then entered into the database and verified by the Epi Info software. A contractor to the University of Maryland developed the Epi Info software is programmed to include range checks, skip patterns, and codes for missing data and don't know answers. If errors are detected, a supervisor will assist with the correction. Monthly reports on coding and editing, data entry and the verification status are prepared and presented at monthly staff meetings and site visits.

NCI IRB Approval:	October 28, 2004
Protocol Number:	05-C-N021

During the study, quality control will consist of data comparisons among interviewers to determine the quantity and quality of information that they have gathered, by evaluating characteristics such as interview duration, number of interview problems reported, number of refusals, distribution of subject answers, and number of missing and incomplete answers. In addition, a small random sample of subjects will be re-contacted to inquire about the interview experience, to note any problems, and to confirm that the interview actually took place. Quality assessment will follow procedures that are already in place for the lung cancer study.

